Our proposed study will add new information to the emerging use of CGM in pregnant women with GDM. First, most studies only use CGM for 48 – 72 hours at a time, while we will be using CGM for 7 day intervals. Both groups will use the same Enlite sensor (Medtronic). The blinded CGM group we will be using the Medtronic iPro2 system (Enlite sensor + transmitter). The real-time CGM group we will be using the 530g system (iPro2 (Enlite sensor + transmitter) + inactivated 530g pump set only to display glucose values, no insulin will be administered). This CGM system has been FDA approved to for up to 7 days between sensor changes.^{26,27} Second, no previous study has used real time CGM in pregnant patients with GDM in the US. We will be the first to describe the use of this technology in this patient population. Third, most of these trials have been performed on populations that are not representative of our patient population at EVMS. This will be the largest US study of CGM in GDM. Fourth wearable medical and fitness technology is already popular, but as both the technology and the demand continues to grow, it will become the future of diabetes management. Studies have already shown that real time CGM is an effective educational and motivational tool in type-1 and type-2 DM.^{28,29}

Research Design and Methods

Subject population

- Subject will be recruited from the EVMS MFM clinics at the main campus (Hofheimer Hall) and Sentara Princess Anne campus. No international sites will be covered by EVMS IRB approval.
- This protocol has been solely developed by EVMS researchers

Inclusion criteria:

- Maternal age 18-45
- Singleton gestation
- Gestational age < 32 weeks gestation at study inclusion
- BMI ≤ 45

- 50g glucose challenge: ≥ 135 mg/dL
- 100 g 3 hr OGTT: ≥ 2 abnormal values using the Carpenter Coustan cut offs (fasting ≥ 95 mg/dL, 1 hr ≥ 180 mg/dL, 2 hr ≥ 155 mg/dL, 3 hr ≥ 140 mg/dL)
- Attended the MFM diabetes education class

Exclusion criteria:

- Maternal age <18, >45
- Multi-fetal gestation
- Gestational age ≥ 32 weeks study inclusion
- BMI > 45
- Pregestational diabetes
- Gestational diabetes diagnosed before 24 weeks
- Did not Attend the diabetes education class
- Known fetal anomaly
- Known fetal aneuploidy
- Required ongoing treatment with medications that can exacerbate hyperglycemia: steroids, hydroxyprogesterone caproate injections (Makena), HARRT HIV medications
- Learning disability
- Concern for non compliance with medical care

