- Imminent preterm delivery due to maternal disease or fetal conditions
- Is not willing to wear CGM

Demographic information collected:

- Maternal age at enrollment (years)
- Gestational age at diagnosis of GDM (weeks)
- Gestational age at study inclusion (weeks)
- Gravidity and parity (G_P_ _ _ _)
- Race or ethnic group (self reported, Black, White, Asian, Hispanic, Other)
- Smoking status (current use in pregnancy at time of enrollment, yes/no)
- Alcohol use (current use in pregnancy at time of enrollment, yes/no)
- BMI at study entry (weight in kg / height in m²)
- History of GDM in a prior pregnancy (yes/no)
- Result of 50g OGTT (mg/dL)
- Results of 3hr 100 g OGTT (mg/dL)
- A1C at time of enrollment
- Other comorbidities including but not limited to: hypertension, autoimmune disease, thyroid dysfunction, polycystic ovarian syndrome, cardiac disease, pulmonary disorders, thromboembolic disorders

Vulnerable populations:

- We will not involve vulnerable populations such as those < 18 years old, prisoners, or mentally impaired in this study.

Study design

- Hypothesis:
 - The increased data and feedback provided by real-time CGM will improve glycemic control in gestational diabetic patients over routine SMBG.
- Primary Outcome:
 - Mean blood glucose (mg/dL) in the real-time CGM group compared to SMBG group during the 4th week of study from data collected on the 6 day of CGM use during that week.
- Covariates
- Glycemic outcomes:
 - Between Groups -Failed dietary therapy (started on medication), time spent in normoglycemia week 1 vs. week 4 (min/day), time spent in hyperglycemia week 1 vs. week 4 (min/day), time spent in hypoglycemia week 1 vs. week 4 (min/day)
 - Within Groups - Time spent in normoglycemia week 1 vs. week 4 (min/day), time spent in hyperglycemia week 1 vs. week 4 (min/day), time spent in hypoglycemia week 1 vs. week 4 (min/day)
- Maternal outcomes :

- BMI at time of delivery (kg/m^2)
- Gestational hypertension (defined as SBP ≥ 140 mm Hg or DBP ≥ 90 mmHg, on 2 occasions at least 4 hrs apart)
- Preeclampsia (defined as gestational hypertension plus either new-onset proteinuria (≥ 300 mg/24 2hrs, protein:creatinine ≥ 0.3 mg/dL), thrombocytopenia (platelet count $< 100,000/\mu\text{L}$), elevated AST or ALT ($> 2x$ upper limit of normal), renal insufficiency (serum creatinine > 1.1 mg/dL or an unexplained doubling of creatinine), pulmonary edema, or cerebral or visual symptoms)
- HbA1C values week 1 compared to week 4 (%)

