- Polyhydramnios (MVP ≥ 8 cm at any point in the pregnancy)
- Cesarean delivery (w/ indication: macrosomia, malpresentation, failed induction, fetal distress, failed TOLAC, scheduled repeat, other)
- IOL (w/ indication)
- Operative vaginal delivery (yes/no) an type (forceps/vacuum)
- Shoulder dystocia (diagnosed clinically)
- Fetal macrosomia ($\geq 4,000\text{g}$ at 38 wk u/s)
- 3rd or 4th degree perineal laceration at time of delivery
- Neonatal outcomes:
 - Gestational age at delivery (weeks, days)
 - Preterm delivery (< 37 weeks gestational age at birth)
 - Birth weight (grams)
 - Perinatal morbidity composite outcome:
 - Hypoglycemia (yes/no): < 2 hrs after birth and before feeding, defined as $< 35\text{mg}/\text{dL}$
 - Hyperbilirubinemia (yes/no): collected 16-36 hrs after birth, defined as $> 95\%$ for any given point after birth requiring phototherapy according to AAP guidelines
 - Birth trauma (yes/no): brachial plexus injury or clavicular, humeral, or skull fracture
 - Intrauterine fetal demise or neonatal death (yes/no): prior to hospital discharge
 - Large for gestational age (yes/no): defined as birth weight $> 90\%$
 - Term infants ($\geq 37'0$) WHO 0-24 months growth charts
 - Boys = $> 4,011$ g
 - Girls = $> 3,852$ g
 - Preterm infants ($< 37'0$) Fenton preterm growth charts
 - Use online calculator with actual gestational age
 - Small for gestational age (yes/no): defined as birth weight $< 10\%$
 - Term infants ($\geq 37'0$) WHO 0-24 months growth chart
 - Boys = $< 2,758$ g
 - Girls = $> <2,678$ g
 - Preterm infants ($< 37'0$) Fenton preterm growth charts
 - Use online calculator with actual gestational age
 - Admission to NICU (yes/no) and length of NICU stay (days)
 - Respiratory distress syndrome (defined as need to supplemental oxygen > 4 hrs after birth)
- Randomization scheme:
 - 40 index cards will be labeled. 20 will have an allocation to one group written on them and the other 20 will have an allocation for the other group written on them for an even number in each group. Each index card will be placed into its own opaque ("security") envelope and sealed. Then the research coordinator will shuffle all envelopes. The research coordinator will label each envelope sequentially from 1 to 40. This number will ensure the generated randomization scheme is maintained and the number will also serve as the participant's study ID. The envelopes will be secured in a locked cabinet in the research office when

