- There is a risk associated with allowing your data to be saved is the release of personal information from your study record. Research team members will strive to protect patient records such as name, address, social security number, phone number and will notify patient if information is breached.

Statistical Analysis Plan

- Sample Size Calculations:
 - Estimated mean blood glucose of a pregnant women with GDM using CGM: 102.6 mg/dL +/- SD 9 mg/dL²⁴
 - Randomized trial, 1:1 allocation, continuous variable outcome
 - Alpha = 0.05
 - Beta = 0.80
 - 10 patients/arm to detect a 20% decrease in mean blood glucose
 - Goal: 20 patients/arm with interim analysis after 10 patients/arm have completed the trial
- Other analysis will be with the guidance and aide of EVMS CHAD:
 - All data will be analyzed with intention to treat. Normality of data will be tested for all continuous variables using the Kolmogorov–Smirnov test. Normally distributed parameters will be presented as mean±SD, and non-normally distributed values are presented as median (range). Categorical data will be reported as frequency and percentage. Parametric (the Student's t-test) or nonparametric (the Mann–Whitney U-test) comparisons will be used based on the distribution of variables. The pre/post change in blood glucose between the two arms will be compared using regression models, when treatment group will be treated as a qualitative independent variable. To assess the significant difference between the two arms adjusting for covariates, ANCOVA model will be used.. A p < 0.05 will be accepted as statistically significant. SAS 9.4 (SAS Institute Inc, Cary, NC) will be used for statistical analysis.

REFERENCES:

1. Bulletins--Obstetrics CoP. Practice Bulletin No. 137: Gestational diabetes mellitus. *Obstet Gynecol*. 2013;122(2 Pt 1):406-416.
2. Moyer VA, Force USPST. Screening for gestational diabetes mellitus: U.S. Preventive Services Task Force recommendation statement. *Ann Intern Med*. 2014;160(6):414-420.
4. Wier LM WE, Burgess J, Elixhauser A. Hospitalizations related to diabetes in pregnancy. In.

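### Polyhydramnios can be scored from scans before allocation, and delivery BMI is not tied to the entry BMI already collected: a low-severity fix to two secondary outcomes

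*Protocol*

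**What the plan says.** Protocol, Study design, Maternal outcomes, lists "BMI at time of delivery (kg/m^2" with no reference to an earlier value. The same list contains "Polyhydramnios (MVP ≥ 8 cm at any point in the pregnancy".

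The entry conditions place allocation well into pregnancy. Inclusion criteria require "Gestational age < 32 weeks gestation at study inclusion", and Exclusion criteria remove "Gestational diabetes diagnosed before 24 weeks". Under Randomization scheme, the envelope is opened only after enrolment.

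Demographic information collected includes "BMI at study entry (weight in kg / height in m²". Polyhydramnios before entry is neither an exclusion criterion nor a named baseline item.

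The Statistical Analysis Plan section of the protocol has three relevant statements:

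- The general between-arm comparison is unadjusted: "Parametric (the Student's t-test) or nonparametric (the Mann–Whitney U-test) comparisons will be used based on the distribution of variables".
- A model for change is written for glucose only: "The pre/post change in blood glucose between the two arms will be compared using regression models".
- Adjustment is foreseen, without saying for what: "To assess the significant difference between the two arms adjusting for covariates, ANCOVA model will be used".

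The Covariates line under Study design has no baseline variable beneath it; the outcome lists follow.

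**The concern.** An outcome in a randomised comparison should be something the allocation could have changed. A polyhydramnios window covering the whole pregnancy reaches back before allocation. A scan at, say, 28 weeks in a woman enrolled at 31 weeks would count, even if the finding had resolved by the time her envelope was opened. Such events add to both arms and pull the observed contrast towards no difference. With 20 women per arm, they can also fall unevenly by chance.

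Delivery BMI has a related but milder weakness. Women may enter with any BMI up to 45, and the intervention lasts four weeks late in pregnancy. Much of the spread in delivery BMI is therefore likely to be spread already present at entry. If the entry value is not used, that spread stays in the error term, and a chance imbalance at entry passes into the result. The protocol ties other outcomes to an early value: HbA1c and time in the glucose ranges are compared between week 1 and week 4. Delivery BMI has a matching entry measurement but no such link.

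At stake is how far two secondary outcomes can be interpreted.

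**Working it through.** The protocol gives no calculation for either outcome, so there is no figure of its own to reproduce. Its only sample-size calculation concerns mean glucose and does not bear on this point.

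**Inputs from the protocol:** 20 women per arm, 1:1 allocation, alpha 0.05, power 0.80 (the figure it labels beta). The test is taken as two-sided, which the protocol does not state.

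**Assumptions, because the protocol gives no values:** between-woman BMI SD 5 to 7 kg/m², the same at entry and delivery; entry-to-delivery correlation r of 0.8 to 0.98; share f of polyhydramnios events before allocation of 0 to 75%.

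**1. Delivery BMI, raw comparison.**

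Standard error of the arm difference = SD × √(2/20). For SD 5, 6 and 7 this is 1.58, 1.90 and 2.21 kg/m².

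Detectable difference (t-test, 80% power, 20 per arm) = 0.909 × SD, giving 4.5, 5.5 and 6.4 kg/m². The normal approximation, (1.96 + 0.84) × SD × √(2/20), gives 4.4, 5.3 and 6.2.

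For scale, at an assumed height of 1.60 to 1.65 m this is about 12 kg (4.55 × 1.60² = 11.6) to 17 kg (6.36 × 1.65² = 17.3). That is a large difference to expect from four weeks of a glucose display.

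**2. Delivery BMI, adjusted for entry BMI.**

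Detectable difference = 0.909 × SD × √(1 − r²).

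| r | √(1 − r²) | Reduction | SD 5 | SD 6 | SD 7 |
|---|---|---|---|---|---|
| 0.80 | 0.600 | 40% | 2.7 | 3.3 | 3.8 |
| 0.90 | 0.436 | 56% | 2.0 | 2.4 | 2.8 |
| 0.95 | 0.312 | 69% | 1.4 | 1.7 | 2.0 |
| 0.98 | 0.199 | 80% | 0.9 | 1.1 | 1.3 |

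The share of delivery-BMI variance explained by entry BMI is r²: 64% at r = 0.80, 90% at 0.95.

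**3. Chance imbalance at entry.**

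With equal SDs, an entry imbalance of one standard error carries r times that amount into delivery BMI: from 0.80 × 1.58 = 1.3 to 0.98 × 2.21 = 2.2 kg/m².

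**4. Polyhydramnios, dilution.**

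Suppose the intervention halved events after allocation and left earlier events untouched. Then the observed risk ratio = f + (1 − f) × 0.5.

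| Share before allocation, f | Observed risk ratio |
|---|---|
| 0% | 0.50 |
| 25% | 0.625 |
| 50% | 0.75 |
| 75% | 0.875 |

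The halving is only an illustration, and the documents do not allow f to be estimated.

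**The case against.** The strongest reply concerns BMI. The protocol collects entry BMI and plans an ANCOVA with covariates. Which covariate enters which secondary model is commonly settled in a separate statistical analysis plan, which may exist and is not at hand. A reader might infer that delivery BMI will be compared without entry BMI. The text does not support that: it is silent on adjusting this outcome and does not rule it out. In a randomised trial, moreover, the expected arm difference in raw delivery BMI equals that in change from entry, so the raw outcome is inefficient but not invalid. All of this stands. What remains is that the outcome is written as a raw value, the comparison written for outcomes in general is unadjusted, and the change model is written for glucose alone.

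A reader might also infer that both outcomes mainly record the woman's state before randomisation. For BMI that is plausible, but only under assumed correlations. For polyhydramnios it cannot be shown: the window also covers all the time from entry to delivery, and the protocol gives neither a rate nor the timing of events.

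Nor is there systematic bias, since randomisation balances earlier states in expectation.

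The objection does not reach the polyhydramnios window. The protocol fixes it explicitly, and no choice of covariates removes events that precede allocation.

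**Conclusion.** The point holds at low severity.

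The polyhydramnios definition is the firmer part. Read as written, it counts events found before allocation. The consequence is dilution and chance noise, of a size that the documents do not allow to be estimated.

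The BMI part is a loss of precision and an exposure to chance imbalance that the protocol leaves open although it already collects the remedy. Under an assumed SD of 5 to 7 kg/m², the raw comparison detects about 4.5 to 6.4 kg/m². Using entry BMI lowers that by 40% to 80% for correlations of 0.8 to 0.98. The exact gain depends on the correlation, but it is substantial across the whole range.

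Both are secondary outcomes. The primary outcome, mean glucose in week 4, and its conclusion are unaffected.

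**What to change.** - **Polyhydramnios:** define the outcome as an MVP of 8 cm or more first found on a scan after randomisation. Record polyhydramnios found earlier as a baseline characteristic and show it by arm.
- **BMI at delivery:** name BMI at study entry as the ANCOVA covariate for this outcome, in the protocol or in the statistical analysis plan if there is one.

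The cost is small. Entry BMI is already collected, so the BMI change is wording only. For polyhydramnios, slightly fewer events may be counted, and scan dates must be taken from the chart: the protocol sets out no scan schedule beyond the 38-week ultrasound for macrosomia.

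### The 10 patients per arm does not follow from the stated inputs, which give 5 per arm by two-sided t-test, and the power is labelled as beta

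*Protocol*

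**What the plan says.** The calculation is in the protocol's Statistical Analysis Plan, under Sample Size Calculations. Its starting point is "Estimated mean blood glucose of a pregnant women with GDM using CGM: 102.6 mg/dL +/- SD 9 mg/dL", and its design is "Randomized trial, 1:1 allocation, continuous variable outcome". Alpha is 0.05 and beta is printed as 0.80. The result is "10 patients/arm to detect a 20% decrease in mean blood glucose". The next line sets the enrolment: "Goal: 20 patients/arm with interim analysis after 10 patients/arm have completed the trial".

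No sidedness, loss allowance or alpha adjustment is given with the calculation. The analysis text below it names Student's t-test and the Mann-Whitney U-test and says that "comparisons will be used based on the distribution of variables". It sets the significance threshold without saying whether it is one- or two-sided: "A p < 0.05 will be accepted as statistically significant". The Primary Outcome under Study design is "Mean blood glucose (mg/dL) in the real-time CGM group compared to SMBG group during the 4th week of study".

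**The concern.** The 10 per arm comes directly after the effect inputs, alpha and beta, so it reads as the result for those inputs. With a target effect of more than two SDs, ten per arm looks too many for 80% power. A beta of 0.80 cannot be right as printed, because beta is the type II error rate.

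This is the only sample size result in the protocol, and the same number marks the interim analysis. If it does not follow from the inputs, the reader cannot tell whether the number, the SD, the effect or the power is misreported, or whether a margin was added without being mentioned. That decides how sensitive the trial is. If the SD is really 9, 20 per arm can detect a fairly small difference. If the authors worked with a larger SD, it cannot.

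**Working it through.** **Inputs (Sample Size Calculations).** Mean 102.6 mg/dL, SD 9 mg/dL, 20% decrease, alpha 0.05, equal arms. The beta line is read as power 0.80. Sidedness is not stated, so two-sided is taken first and one-sided is also tried.

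**Effect.** 0.20 × 102.6 = 20.52 mg/dL, and d = 20.52/9 = 2.28.

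**Attempt to reproduce 10 per arm.** The normal approximation gives n = 2(1.960 + 0.842)²/2.28² = 3.02, so 4 per arm. Exact power for the two-sample t-test uses the noncentral t with 2n − 2 degrees of freedom and noncentrality d√(n/2). Exact Mann-Whitney power was simulated on normal data.

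| n per arm | two-sided t-test | two-sided exact Mann-Whitney |
|---|---|---|
| 4 | 76.6% | about 60% |
| 5 | 88.3% | about 79% |
| 6 | 94.4% | about 91% |
| 10 | 99.8% | 99.6% |

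The smallest n reaching 80% is 5 per arm by t-test and 6 per arm by Mann-Whitney. The stated 10 is not reproduced.

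**Other readings of the same inputs.** None comes closer to 10.
- One-sided 0.05, t-test: 74.1% at 3 and 88.3% at 4, so 4 per arm.
- 102.6 as the mean of the monitored arm: control 102.6/0.8 = 128.25, difference 25.65, d = 2.85. Two-sided power is 74.3% at 3 and 91.6% at 4, so 4 per arm.
- Beta taken literally as 0.80, i.e. 20% power: 26.3% at 2, so 2 per arm.

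**What would give 10 per arm.** Each of these needs something the protocol does not state (two-sided t-test).
- At 80% power, an SD above 14.58 and up to 15.49 instead of 9.
- An uncorrelated change-score SD of 9√2 = 12.73 with 90% power (89.4% at 9, 92.6% at 10). At 80% power that SD gives 8 per arm. The analysis text does mention change ("The pre/post change in blood glucose between the two arms will be compared using regression models"), but the primary outcome is the week-4 mean.
- SD 9 with 99% power (9 per arm) and a 10% loss allowance: 9/0.9 = 10.
- SD 9 with 80% power and a 50% loss allowance: 5/0.5 = 10.
- A total (5 + 5 = 10) printed as a per-arm number.

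The protocol does not show which of these applies, if any.

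**Difference detectable at 80% power, two-sided 0.05.**
- SD 9, 10 per arm: d = 1.325, so 1.325 × 9 = 11.9 mg/dL (11.6% of 102.6).
- SD 9, 20 per arm: d = 0.909, so 0.909 × 9 = 8.2 mg/dL (8.0%).
- SD 15, for which 10 per arm would be the correct answer to the 20% question, 20 per arm: 0.909 × 15 = 13.6 mg/dL (13.3%).

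**The case against.** The sentence does not call 10 a minimum, and ten per arm does detect a 20% decrease, with 99.8% power. Ten could be 5 with an unmentioned margin. The Risk section gives a reason for one: a participant who has trouble with the device has it removed and need not wear another, which could cost week-4 data. Enrolment is fixed at 20 per arm, the interim at 10 is simply half of that, and any statistician will read the beta line as 80% power.

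Most of this stands. The statement is not a false claim of capability, and a margin is possible, so the printed figures need not themselves be wrong. It does not remove the point. No margin is stated with the calculation, and the visible increase, from 10 to 20, comes afterwards on its own line. The beta label is wrong however easily it is understood.

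A fair caution concerns calling the discrepancy conservative. That holds only for SD 9 and a 20% fall, from 102.6 to about 82.1 mg/dL. The protocol's Background reports that the study cited for the mean and SD, in 340 women with GDM, found no significant difference in mean blood glucose. The generous power for 20% therefore says nothing about power for a smaller effect.

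**Conclusion.** The concern holds and is minor. On the stated inputs the requirement is 5 per arm by two-sided t-test, or about 6 by exact Mann-Whitney, against the printed 10. No reading of those inputs reaches 10. The power value is printed under the name of beta.

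The discrepancy is on the safe side for the stated effect and SD: the planned 20 per arm is four times the two-sided t-test requirement. Enrolment and validity are not affected. What is lost is traceability, and with it a clear statement of what 20 per arm can detect. That is about 8.2 mg/dL at SD 9 but about 13.6 mg/dL at SD 15.

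These results assume normal data with equal SDs and 80% intended power. The detectable differences at 20 per arm also assume that all 40 participants are evaluable and that the final test keeps the full two-sided 0.05 despite the interim analysis. Where the 10 came from cannot be settled from the protocol.

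**What to change.** Keep 20 per arm. Replace the beta line with power 0.80 (beta 0.20), and state whether alpha is one- or two-sided. Then take one of two routes.

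- **If SD 9 is the intended input and no margin was applied:** replace the 10 per arm line with 5 per arm (two-sided t-test). Add the difference detectable at 20 per arm, about 8.2 mg/dL (8.0%), with the conditions that all 40 are evaluable and the final test uses the full 0.05. The detectable difference is the more useful of the two figures.
- **If 10 came from something else** (a larger SD, a change-score SD, higher power or a loss allowance): state it, show the calculation, and recompute the difference detectable at 20 per arm on that basis.

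The cost is protocol wording only. Enrolment, endpoint and test stay as they are.

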not needed. Only after a participant has been enrolled into the study will an envelope be opened and the patient allocated to a group.

Procedures

- Procedures
- [name] will review charts of new Gestational Diabetes patients whom are scheduled to attend the gestational diabetes classes at Eastern Virginia Medical School (Mondays) and EVMS Sentara Princess Anne MFM Clinic (Fridays). He will select those patients who meet the study criteria based on the inclusion/exclusion of the study. He will then give that information to Research Coordinator, [name]. [name] will call patients a day before their scheduled Diabetes class to discuss this study. If patient agrees to participate, [name] will meet them right before class to enroll (review and sign consent forms). [name] will do the same for Sentara Princess Anne patients.
- Patients will be randomized to two arms: Traditional Management (20 patients); using the Ipro2 CGM and CGM management (20 patients); using the “real time” CGM. [name] will randomize patients in arms according to names drawn from an envelope during the time of consent. Research activities will occur at standard of care clinical visits. Patients are required to attend research study visits every 7 days for 4 weeks.
- During each visit data such as demographic data, glycemic levels, primary and secondary maternal and neonatal outcomes will be collected. At each visit CGM will be downloaded, a new sensor will be placed for the next 7 days, clinicians will manage GDM per EVMS GDM protocols, and DM will provide dietary reviews/education. [name] will download CGM, add interval data points to database and replace CGM for EVMS patients. [name] will do the same for EVMS Sentara (Princess Anne) patients. Data will be printed and transferred to data collection sheets. All data from the forms will be uploaded into a de-identified electronic database (Redcap, EVMS, set up by EVMS CHAD). All forms will be placed in the patient’s research folder.
- Patients charts will be kept locked in a file cabinet in the research coordinator’s office. Only members of the study will have access to this file cabinet.
- Outcome data will be collected at the completion of study. The data from the CGM reports will not be shared with the clinical provider during the clinic visits.

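### An interim look at 10 per arm and a final analysis at 20 per arm share a single p < 0.05 threshold; if glucose is tested at both, type I error is about 8.3%, not 5%

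*Protocol*

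**What the plan says.** All the relevant text on error control is in the protocol's Statistical Analysis Plan section.

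- Under Sample Size Calculations, alpha is 0.05 and the required size is given as "10 patients/arm to detect a 20% decrease in mean blood glucose". The next line reads "Goal: 20 patients/arm with interim analysis after 10 patients/arm have completed the trial".
- The inputs are "Estimated mean blood glucose of a pregnant women with GDM using CGM: 102.6 mg/dL +/- SD 9 mg/dL", with 1:1 allocation. Beta is written as 0.80, which I read as 80% power.
- Under the bullet on other analyses, the only threshold is "A p < 0.05 will be accepted as statistically significant". Between-arm comparisons use Student's t-test or the Mann-Whitney test, depending on the distribution.
- Under Study design, the primary outcome is "Mean blood glucose (mg/dL) in the real-time CGM group compared to SMBG group during the 4th week of study".

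The interim is mentioned nowhere else. The protocol gives no purpose for it, no stopping rule, no interim boundary and no adjusted final level.

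**The concern.** A scheduled look halfway through and a single unadjusted threshold do not fit with a stated alpha of 0.05 if the primary outcome is tested at both looks.

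Three features make an efficacy test the natural reading of the interim:

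- It falls at exactly the number per arm that the plan calls sufficient for its target effect.
- It is triggered when patients have completed the trial, so their week-4 glucose is available.
- Nothing in the protocol suggests a safety or futility look. The Risk section has no stopping rule.

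Two things are at stake. The first is the false-positive rate for the primary outcome. The second is the size of any effect reported after an early claim, because trials that cross a threshold early tend to have estimates that are too large. Silence about the purpose also leaves room to decide what the interim was for after its results are known.

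**Working it through.** **Inputs from the protocol:** mean 102.6 mg/dL, SD 9, target fall 20%, alpha 0.05, looks at 10 and 20 per arm, t-test. **Assumptions:** two-sided testing (sidedness is not stated); true differences of 8.2 and 10.26 mg/dL where used below.

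**1. The plan's own sample size.** The target difference is 0.20 × 102.6 = 20.52 mg/dL, which is 20.52 / 9 = 2.28 SD. The normal approximation gives n = 2 × (1.960 + 0.842)² × 9² / 20.52² ≈ 3.02, so 4 per arm. With the t-test it is 5 (power 0.77 at 4 and 0.88 at 5). The stated 10 per arm is not reproduced. That is a separate matter: the error rate below depends only on the threshold and the timing of the looks.

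**2. Power at the interim.** At 10 per arm the noncentrality is 20.52 / (9 × √(2/10)) = 5.10 on 18 degrees of freedom, which gives power of 99.8%. On the plan's own figures, the interim is fully able to serve as an efficacy test.

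**3. Type I error with two looks.** The interim uses 10/20 = 0.5 of the information, so the two test statistics have correlation √0.5 = 0.707 under the null. The overall error is 1 − P(|Z₁| ≤ c₁ and |Z₂| ≤ c₂). The simulation used 1,000,000 null trials with t-tests at both looks.

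| Rule (interim p, final p) | Bivariate normal | Simulated t-tests |
|---|---|---|
| 0.05, 0.05 | 0.0831 | 0.084 |
| O'Brien-Fleming 0.0052, 0.048 | 0.0500 | 0.050 |
| Pocock 0.0294, 0.0294 | 0.0500 | 0.051 |

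1 / 0.0831 ≈ 12, so about 1 null trial in 12 is positive. With one-sided 0.05 at both looks the error would be 0.080, so sidedness does not change the conclusion.

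**4. Overestimation after an early claim at p < 0.05 (SD 9, simulated).**

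| True difference (mg/dL) | Chance of interim p < 0.05 | Mean estimate given an early claim (mg/dL) | Excess |
|---|---|---|---|
| 20.52 (protocol's target) | 99.8% | 20.55 | 0.1% |
| 10.26 (assumed, half the target) | 67% | 12.29 | 20% |
| 8.2 (assumed; 80% power at 20 per arm) | 49% | 11.31 | 38% |

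**5. Power under each rule.**

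| True difference (mg/dL) | Single final test | Two looks at 0.05 | O'Brien-Fleming | Pocock |
|---|---|---|---|---|
| 8.2 | 80.2% | 82.2% | 79.8% | 75.2% |
| 10.26 | 94.0% | 94.7% | 93.8% | 91.5% |
| 20.52 | >99.9% | >99.9% | >99.9% | >99.9% |

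**The case against.** The strongest reply is that the protocol never says glucose will be tested at the interim, or that success may be claimed there. The look could be descriptive, a check of the assumed SD of 9, or a feasibility check. The randomization scheme prepares all 40 allocations and gives no route to stopping early. The p < 0.05 rule is in a different bullet from the interim, and interim boundaries are often left to a separate statistical analysis plan.

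Part of this stands. The 8.3% is the error of one reading of the plan, not of a rule it spells out, and a look with no efficacy claim inflates nothing.

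The appeal to a separate document is weaker. This section is itself headed as the statistical analysis plan. It schedules the look and fixes 0.05 with no exception, so a boundary set elsewhere would conflict with it.

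Three smaller points are also fair:

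- The overestimation and power comparisons away from 20.52 mg/dL rest on assumed effects. At the protocol's own target they are negligible.
- A stricter boundary makes early claims rarer but more exaggerated when they occur. At 8.2 mg/dL the mean estimate after an O'Brien-Fleming early claim is about 13.6 mg/dL (+66%), against +38% at 0.05.
- Allocation is not blocked, so both arms will reach 10 at somewhat more than 20 completers: about 22 on average if patients complete in allocation order. This has little effect on the 8.3%.

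**Conclusion.** The concern holds as a conditional statement. Applying the stated threshold at both stated looks, with success claimable at either, raises the two-sided type I error from 5% to 8.3% (8.4% by simulated t-tests). This assumes a between-arm test of mean glucose at half and at full information. It does not depend on the assumed effect or SD.

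The overestimation is secondary. It is 0.1% at the protocol's target and becomes material only if the true difference is much smaller.

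This should be fixed, and the fix is easy. The ambiguity bears on error control for the primary outcome, but it does not make the trial invalid.

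**What to change.** State the purpose of the interim in the Statistical Analysis Plan section before any interim data are seen. Either:

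- **(a)** state that no between-arm efficacy claim on glucose can be made at 10 per arm, and keep 0.05 for the final test; or
- **(b)** pre-specify a group-sequential boundary, for example O'Brien-Fleming (p < 0.0052 at the interim, p < 0.048 at the final) or Pocock (p < 0.0294 at each look). Add that an estimate reported after an early claim may be too large. The boundary makes such claims rarer (17% of trials against 49% at an assumed 8.2 mg/dL) but does not remove the exaggeration.

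The cost is one or two sentences. Option (a) loses no power against a single final test. At 8.2 mg/dL, O'Brien-Fleming loses 80.2 − 79.8 = 0.4 points against a single final test and 82.2 − 79.8 = 2.4 points against two unadjusted looks. Pocock loses 80.2 − 75.2 = 5.0 points against a single final test. At the protocol's own 20.52 mg/dL the loss is negligible under either boundary.
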